4.4 Safety Evaluation

The evaluation of safety variables (as defined in Section 2.5) will be performed based on the SAS (or FAS, if both analysis sets include the same patients).

Adverse Events

Adverse events (AE) will be coded according to the Medical Dictionary for Regulatory Activities (MedDRA).

TEAEs will be tabulated and non-TEAEs will be listed.

AEs will be categorized as non-TE or TE using the start date of the AE and the date of first administration of trial product as follows:

Non-TEAEs are defined as AEs with onset date prior to the day of first administration of trial product.

Treatment-emergent AEs (TEAEs) are defined as AEs with onset date on or after the day of first administration of trial product.

In case of an incomplete or missing AE start date, the AE will be categorized as TE (worst case).

An AE overview summary table will be prepared for the following AE categories and will present the number and percentage of patients reporting at least one AE in this category and the number of events reported for this category:

- TEAEs
- TE adverse drug reactions (ADRs) [ADRs are defined as events with relationship to study treatment, i.e. judged by the Investigator as possible or probable]
- TE serious adverse events (SAEs)
- TEAEs leading to permanent discontinuation of study treatment.

In addition, separate summary tables will be generated for each of the above AE categories. These will present the number of events as well as number and percentage of patients with an AE in the respective category classified in MedDRA system organ classes (SOCs) and preferred terms (PTs).

An overview summary table will present the number and percentage of patients with at least one TEAE by severity, seriousness, relationship, action taken with study treatment, and outcome.

In addition, summary tables will present the number and percentage of patients with each PT grouped by severity, seriousness, relationship, action taken with study treatment, and outcome.

Individual patient data listings will be provided for AEs, SAEs (including deaths), ADRs, Adverse events of special interest (AESIs) [defined as neoplasms (malignant and benign), suspicion of liver injury, pancreatitis and cholecystitis], and for AEs leading to permanent discontinuation of study treatment. In these patient data listings, AEs will be flagged as non-TE and TE.

Non-TEAEs will in addition be listed separately based on all patients included into the trial.

• Vital signs (body temperature, systolic/diastolic blood pressure, pulse rate) and body weight

For vital signs and body weight, standard descriptive summary statistics will be calculated for values at visits and for absolute changes from baseline.

Physical Examination

This will be summarized by the number and percentage of patients with normal/abnormal findings per body system at each visit.

• Electrocardiograms (ECG)

For the ECG parameters (heart rate, PR, QRS, QT, QTcF, RR), standard descriptive summary statistics will be calculated for values at visits and for absolute changes from baseline. Additional ECGs performed for cause as needed to evaluate AEs will only be listed.

• Laboratory parameters (hematology, biochemistry and urinalysis)

Values and absolute changes from baseline to post-baseline visits with an assessment of the respective clinical laboratory parameter (as defined in Section 2.1.2.1) will be summarized by visit using descriptive statistics. Further details on the handling of laboratory parameters are described in Section 2.1.3.

• Immunogenicity Assessments

A serum sample is defined as anti-drug antibody (ADA)-positive if results of the antiglepaglutide antibody screening and confirmatory assays are positive. If positive, a titer (highest dilution factor that still yields a positive reading) will be reported. Patients without any ADA data (evaluable samples) will be excluded from the analysis.

- 1. Pre-existing ADA (Yes/No) is defined, at the patient level, by the ADA status at trial baseline (i.e. Day 4 of MBS at V1), according to the presence or absence of ADA. This will be missing for patients without a valid ADA assessment at baseline.
- 2. A treatment-boosted ADA positive patient (Yes/No) is defined, at the patient level, by an at least 4 fold increase from trial baseline in ADA-titer at any visit for patients with pre-existing ADA (and a titer at baseline). Thus, it will be missing, if pre-existing ADA is missing or no post-baseline sample is available. It will be "Yes", if the sample at any visit shows a 4 fold increase from baseline and "No" otherwise.
- 3. A treatment-induced ADA positive patient (Yes/No) is defined, at the patient level, by a positive ADA sample at any visit without pre-existing ADA (based on a negative baseline ADA measurement). Thus, it will be missing, if pre-existing ADA is missing or if no post-baseline sample is available. It will be "Yes", if pre-existing ADA is "No" and the sample at any visit is ADA-positive. Otherwise, it will be "No".
- 4. An ADA positive patient (Yes/No) is defined by being either treatment-boosted or treatment-induced ADA positive during the trial (for patients with a baseline ADA measurement). Thus, it will be missing, if pre-existing ADA is missing or if no post-baseline sample is available.

Confirmed positive ADA samples will be further evaluated in three different ADA characterization assays: for in vitro glepaglutide neutralizing potential (NAb), for reactivity to the predominant metabolite (M2) and for cross-reactivity towards GLP-2. In case of a positive result in the ADA characterization assays, a titer will be estimated.

For ADA negative samples, the missing assessments for in vitro glepaglutide neutralizing potential (NAb), for reactivity to the predominant metabolite (M2) and for cross-reactivity towards GLP-2 will be considered negative in all below presentations.

In case of positive results at study baseline (Day 1) in the ADA characterization assays ('Pre-existing NAb', 'pre-existing M2 reactivity', 'pre-existing GLP-2 cross-reactivity'), the

definitions and calculations for pre-existing ADA and treatment boosted ADA will correspondingly apply.

In case of a negative assessment in either of the four assays (ADA, NAb, M2 reactivity and GLP-2 cross-reactivity) the titer value will be set to ¼ MRD (Minimal Required Dilution) for illustration purposes.

Immunogenicity Statistical Methodology

All analyses will be done for all four ADA assessments (ADA, NAb, M2 reactivity and GLP-2 cross-reactivity), unless otherwise specified.

Analysis of ADA positive patients by visit will be done separately and combined, for patients with and without pre-existing ADA. For patients with pre-existing ADA, 'treatment-boosted ADA by sample' is defined as a post-baseline ADA positive sample at a given visit with a titer that has increased at least 4-fold from baseline. For patients without pre-existing ADA, 'treatment-induced ADA by sample' is defined as a post-baseline ADA positive sample at a given visit. For all patients, "ADA positive by sample" is defined as either treatment-boosted by sample or treatment-induced by sample.

The overall anti-glepaglutide antibody incidences (all ADA positive patients) will be presented.

The percentage of "ADA positive by sample" patients will be summarized by visit.

Similar tables will be made separately for "treatment boosted ADA by sample" and "treatment induced ADA by sample", if both types are observed.

For all treatment induced ADA positive patients, the titer levels will be summarized by visit using descriptive statistics including median, geometric mean, geometric CV%, inter-quartile range, minimum, maximum, and number of observations (positive samples only).

For all treatment boosted ADA positive patients (if applicable), the titer levels and fold increases from baseline of titers will be summarized by visit using descriptive statistics including median, geometric mean, geometric CV%, inter-quartile range, minimum, maximum, and number of observations (positive samples only).

All immunogenicity data will be listed, including corresponding PK concentrations.

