### 8.4.1 Time Period and Frequency for Collecting AE and SAE Information

All AEs, whether serious or non-serious, must be collected from the time a signed and dated informed consent form is obtained until the follow-up visit.

Patients will be observed for any signs or symptoms and asked about their condition by open questions, such as "How have you been feeling since you were last asked?" at each contact with the trial site. Patients will also be encouraged to spontaneously inform the Investigator of any signs or symptoms occurring at any other time during the trial.

All AEs, regardless of seriousness, severity, or presumed relationship to trial product, must be recorded and evaluated by the Investigator. Whenever possible, diagnoses should be given when signs and symptoms are due to a common etiology. If no diagnosis can be made, the Investigator

should record each sign and symptom as individual AEs. Investigators must record their opinion concerning the relationship of the AE to the trial product. All measures required for AE management must be recorded in the source document and reported according to Sponsor instructions.

- All AEs will be reported in the eCRF.
- AE information should as a minimum include the following:
  - o Date and time of onset.
  - o Date and time of Investigators first information about the AE.
  - Seriousness.
  - o Severity.
  - o Causal relationship with trial product.
  - o Measures taken due to AE.
  - o Interruption or discontinuation of treatment with trial product.
  - Date of resolution and final outcome.

All AEs will be coded using the Medical Dictionary for Regulatory Activities (MedDRA). 1

All SAEs will be recorded and reported to Pharmalex immediately and under no circumstance should this exceed **24 hours**, as indicated in Appendix 3: Adverse Events: Definitions and Procedures for Recording, Evaluating, Follow-up, and Reporting. The Investigator will submit any updated information on SAEs to Pharmalex within 24 hours of it being available.

Investigators are not obligated to actively seek AE or SAE after conclusion of the trial participation. However, if the Investigator learns of any SAE, including a death, at any time after a patient has been discharged from the trial, and he/she considers the event to be reasonably related to the trial intervention or trial participation, the Investigator must promptly notify the Sponsor.

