### 8.4.3 Follow-up of AEs and SAEs

After the initial AE/SAE report, the Investigator is required to proactively follow each patient at subsequent visits/contacts. All SAEs including AESIs (as defined in Section 8.4.6) will be followed up until resolution, stabilization, the event is otherwise explained, or the subject is lost to follow-up (as defined in Section 7.3). As the case for initial AEs/SAEs, follow-up information is reported in the eCRF. Follow-up questions to Investigators regarding SAEs are queried directly by Pharmalex to the Investigator. Further information on follow-up procedures is provided in Section 10.3 (Appendix 3).

Follow-up information must be reported according to the following:

<sup>1 The most current version at the beginning of the trial.

• SAEs: All SAEs must be followed until the outcome of the events is "recovered/resolved", "recovered/resolved with sequelae", or "fatal", and until all queries have been resolved. Cases of chronic conditions, cancer, or AEs ongoing at time of death (where death is due to another AE) may be closed with the outcome "recovering/resolving" or "not recovered/not resolved". Cases can be closed with the outcome of "recovering/resolving" when the patient has completed the follow-up period and is expected by the Investigator to recover.

The SAE follow-up information should only include new (e.g., corrections or additional) information and must be reported **within 24 hours** of the Investigator's first knowledge of the information. This is also the case for previous non-serious AEs which subsequently become SAEs.

• Non-serious AEs: Non-serious AEs must be followed until the outcome of the event is "recovering/resolving", "recovered/resolved", or "recovered/resolved with sequelae" or until the end of the follow-up period stated in the protocol, whichever comes first, and until all queries related to these AEs have been resolved. Cases of chronic conditions, cancer, or AEs ongoing at time of death (where death is due to another AE) may be closed with the outcome of "recovering/resolving" or "not recovered/not resolved". Cases can be closed with the outcome of "recovering/resolving" when patient has completed the follow-up period and is expected by the Investigator to recover.

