The Investigator must ensure that the worst-case severity and seriousness of an event is kept throughout the trial, i.e. if the severity of an AE changes over time then it should be reported as a single AE with worst-case severity. A worsening of an unresolved AE must be reported as follow-up with re-assessment of severity and/or seriousness of the event.

If an AE is resolved and re-appears later then it should be reported as a new AE.

Queries or follow-up requests must be responded within 14 calendar days from the date of receipt of the request, unless otherwise specified in the follow-up request.

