# 9.4.6 Other Safety Analyzes

All safety analyzes will be made on the SAS. The standard safety assessments (AEs [only treatment-emergent AEs will be tabulated, whereas non-TE AEs will be listed], safety laboratory parameters, vital signs, etc.) will be reported descriptively; including any notable changes of clinical interest in laboratory parameters. Treatment-emergent AEs are defined as AEs with onset date on or after the day of first administration of trial product.

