2.5 Safety Endpoints and Variables

Safety endpoints are:

- Treatment-emergent adverse events (TEAEs) until follow-up at Week 56
- Immunogenicity (anti-glepaglutide antibodies, reactivity to M2 (referred to as ZP1848₁₋₃₄ in the clinical trial protocol), cross-reactivity to glucagon-like peptide [GLP]-2, glepaglutide neutralizing antibodies) at baseline (W0), Week 4, 12, 24, 52, and 56.

The following safety variables will be analyzed in this context:

TEAEs

TEAEs are defined as AEs with onset date on or after the day of first administration of trial product.

Immunogenicity

Immunogenicity will be assessed by the following:

- Anti-glepaglutide antibodies
- Reactivity to M2
- Cross-reactivity to GLP-2
- Glepaglutide neutralizing antibodies

and will be evaluated at Baseline, Week 4, Week 12, Week 24, Week 52 (EOT), and FU.

In addition, the following other safety variables will be analyzed:

• Vital signs (body temperature, systolic/diastolic blood pressure, pulse rate) and body weight

Values and absolute changes from baseline to post-baseline visits with assessment of vital signs (as defined in Section 2.1.2.1) will be summarized by visit using descriptive statistics.

• Clinical laboratory tests (hematology, biochemistry, and urinalysis)

Values and absolute changes from baseline to post-baseline visits with an assessment of the respective clinical laboratory parameter (as defined in Section 2.1.2.1) will be summarized by visit using descriptive statistics.

• Physical Examination

This will be summarized by presenting number and percentage of patients with normal/abnormal findings per body system at each visit.

• Electrocardiogram

Values and absolute changes from baseline to post-baseline visits with assessment of ECG (as defined in Section 2.1.2.1) will be summarized by visit using descriptive statistics.

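### An adverse event that begins between consent and first dose and worsens on treatment is classed as not treatment-emergent and drops out of the TEAE tables

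*SAP*

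**What the plan says.** **Classification.** Protocol 9.4.6: "Treatment-emergent AEs are defined as AEs with onset date on or after the day of first administration of trial product". SAP 2.5 and 4.4 repeat this rule, and SAP 4.4 names the only inputs: "AEs will be categorized as non-TE or TE using the start date of the AE and the date of first administration of trial product". The complement is also explicit: "Non-TEAEs are defined as AEs with onset date prior to the day of first administration of trial product". None of the three sections mentions worsening.

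**Collection.** Protocol 8.4.1 says that AEs "must be collected from the time a signed and dated informed consent form is obtained until the follow-up visit", so records with a pre-dose onset can exist.

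**Recording.** Protocol 8.4.3 says that "if the severity of an AE changes over time then it should be reported as a single AE with worst-case severity". It goes on to require that worsening of an unresolved event be sent as follow-up, with severity and seriousness re-assessed. On the content and 24-hour timing of SAE follow-up it adds: "This is also the case for previous non-serious AEs which subsequently become SAEs". Protocol 10.3.3 puts updates into the eCRF entry that was completed at the start.

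**Reporting.** SAP 4.4 tabulates treatment-emergent events and gives the others in listings only.

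**The concern.** Each rule is workable alone. Together they let the date on which an event began settle how its later course on drug is counted. Suppose a new mild symptom starts during screening, is still present at first dose, and in Week 3 becomes severe and leads to admission. The protocol asks for one record, with the screening onset and the Week 3 severity and seriousness. The SAP then classes the whole record as pre-treatment.

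TEAEs are a named safety endpoint, and this single-arm trial has no control group against which a shortfall could be seen in the tables. The error also runs one way: the rule can make treatment-emergent counts too low, never too high. A second effect is misattribution. Because the record keeps only the worst severity, a listing shows a severe or serious event with a pre-dose onset, and a reader could take it as severe before any drug was given.

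**Working it through.** No figure in the plan needs reproducing, since this is a classification rule. The check follows one hypothetical record through the documents.

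1. **Onset.** The event starts after consent and before the day of first dose, with a complete start date. It is collected (protocol 8.4.1).
2. **Worsening on treatment.** The event is unresolved when it becomes more severe or serious. Under protocol 8.4.3 this is follow-up of the same event, kept at worst case; under 10.3.3 it is entered in the original eCRF record. Nothing in these sections moves the onset date.
3. **Classification.** SAP 4.4 compares start date with first-dose date. The start date is earlier, so the event is not treatment-emergent.
4. **Tables.** SAP 4.4 restricts the overview (Table 3-1.1), the TEAE, adverse drug reaction and serious-event tables (3-1.2 to 3-1.4), and the tables by severity, seriousness, relationship, action taken and outcome (3-1.6 to 3-1.11) to treatment-emergent events. The record is in none of them.
5. **Discontinuation table.** SAP 4.4 limits this to TEAEs, but the Appendix A title of Table 3-1.5 carries no such limit. The documents do not settle whether the record would appear there.
6. **Listings.** The record appears in the AE listing and, where it qualifies, the SAE, ADR, AESI and discontinuation listings, flagged as not treatment-emergent. It also appears in Listing 3-6, whose title describes its contents as pre-treatment.

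**What the rules already handle**

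| Situation | Rule | Result |
|---|---|---|
| Worsening of a condition recorded as medical history or concomitant illness | Clinically significant worsening is an AE in its own right (protocol 10.3.1) | Onset on treatment, so a TEAE |
| Event resolves, then recurs | New AE (protocol 8.4.3) | TEAE if it recurs on or after first dose |
| Incomplete or missing start date | Worst-case rule (SAP 4.4) | TEAE |
| Onset on the dosing day | Onset rule | TEAE |
| Onset between consent and the day before first dose, unresolved, then worsens on treatment | Single record (protocol 8.4.3) | Not a TEAE: the gap |

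**Length of the onset window.** Screening lasts up to 21 days before Visit 1 (protocol Table 1), and the first dose comes on Day 4 of the Visit 1 stay (protocol Table 2), about 3 days after admission: 21 + 3 = about 24 days. Against the maximum trial period of 59 weeks, 59 × 7 = 413 days, and 24/413 = 5.8%.

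**Effect of one omitted patient on an incidence row**, as an upper bound of 1/n, with n from protocol 4.1 and 9.2:

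- n = 6: 1/6 = 16.7 percentage points
- n = 10: 1/10 = 10.0 percentage points
- n = 16: 1/16 = 6.3 percentage points

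The row changes only if that patient has no other event counted in it.

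**The case against.** The strongest reply is that the gap is small and the data are not hidden. Much of it stands.

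- **Ordinary SBS symptoms.** A reader might infer that the rule loses the very symptoms these patients bring into the trial, since the common phase 2 events (nausea, abdominal pain, distension) resemble the disease. The documents do not support that. Protocol 10.3.1 keeps pre-existing conditions out of the AE record and makes their clinically significant worsening a new AE. Only events that newly start after consent are exposed.
- **Visibility.** A reader might infer that nothing would reveal the omission. The flagged listings would, and with about 10 patients they can be read in full. SAEs are also reported within 24 hours, and the sponsor's safety committee reviews all AEs. The fault is in the tables and the labelling.
- **Discontinuations.** A reader might infer that such an event is missing from every discontinuation summary. Table 1-1.3 tabulates reasons for premature discontinuation without a treatment-emergent limit, and the scope of Table 3-1.5 is inconsistent.
- **Size.** The 1/n figures bound the effect of one patient on one row. They do not estimate bias.
- **Evidence.** Protocol 8.4.3 does not say in words that the original onset date is kept. That is an inference, though the natural one from a single record updated in place. The sentence about non-serious events becoming serious concerns follow-up content and timing, so it only supports the point.

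None of this closes the gap. The same worsening is tabulated if the condition began before consent and omitted if it began the day after. An event with an unknown start date is counted as a precaution, while one known to have worsened on drug is not.

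**Conclusion.** The plan is wrong as written, within a narrow scope. A new AE with a complete onset date between consent and first dose, still unresolved at dosing, that increases in severity or becomes serious on treatment is classed as not treatment-emergent and omitted from the TEAE, treatment-emergent ADR, treatment-emergent SAE and breakdown tables. Its on-drug severity is then visible only in listings.

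The documents give no basis for how often this will happen, and it may not happen at all. This rests on two assumptions: that follow-up leaves the onset date unchanged, and that consent is signed no earlier than the start of the 21-day screening window. The point merits correction because a stated rule yields a wrong count for a safety endpoint and the remedy is cheap. It does not support a claim that the safety tables are broadly unreliable.

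**What to change.** 1. **Protocol 8.4.3.** When an AE that began before first dose increases in severity or seriousness on or after first dose, enter a new AE record dated at the worsening and linked to the original. The original keeps its pre-dose severity and seriousness. Keep the single-record rule for AEs that start after first dose.
2. **Protocol 9.4.6, SAP 2.5 and SAP 4.4.** State that TEAEs include pre-dose AEs that worsen on or after first dose, identified by that new record. The existing onset rule then classes it as treatment-emergent, and the tables count it once because the original stays outside them.
3. **Records already entered as one AE.** The minimum AE data in protocol 8.4.1 hold no date of severity change, so use the follow-up history to date the worsening. If it cannot be dated, count the event as treatment-emergent, in line with the SAP's rule for missing start dates.
4. **Table 3-1.5.** Reconcile the Appendix A title with SAP 4.4.

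**Cost.** A protocol amendment with the ethics committee step in protocol 10.1.1, matching SAP wording, one eCRF instruction, and a review of pre-dose AE records. TEAE counts may be slightly higher.

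### SAP 4.4 counts every AE with an incomplete start date as treatment-emergent, even when the known month or the stop date shows it began before first dose

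*SAP*

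**What the plan says.** SAP 4.4 (Adverse Events) classifies each event from two dates: "AEs will be categorized as non-TE or TE using the start date of the AE and the date of first administration of trial product". It gives both definitions. For the pre-dose group: "Non-TEAEs are defined as AEs with onset date prior to the day of first administration of trial product". For the other: "Treatment-emergent AEs (TEAEs) are defined as AEs with onset date on or after the day of first administration of trial product". It then adds the fallback: "In case of an incomplete or missing AE start date, the AE will be categorized as TE (worst case").

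Nothing elsewhere qualifies the fallback. Protocol 9.4.6 and SAP 2.5 repeat the treatment-emergent definition without a rule for partial dates. SAP 4.5 says only that missing values are not replaced unless specified otherwise. SAP 6, on changes from the protocol, does not mention the matter.

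Protocol 8.4.1 makes pre-dose events part of the database, since AEs "must be collected from the time a signed and dated informed consent form is obtained until the follow-up visit". The same section lists the minimum information for each AE, which includes "Date and time of onset" and "Date of resolution and final outcome". So a stop date is normally available when the start date is incomplete.

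**The concern.** A worst-case assignment is reasonable when the data cannot say whether an event began before or after first dose. The SAP rule goes further, because it applies as soon as any part of the start date is missing and ignores the parts that are known. An event recorded as starting in March, day unknown, in a patient first dosed in April began before treatment on any reading, yet it is tabulated as treatment-emergent. The same happens to an event with a partial or missing start date that resolved before first dose.

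TEAEs up to Week 56 are a stated safety endpoint. The trial has one arm and few patients, so no control rate offsets a misplaced event. Such an event would enter the TEAE tables, carry the wrong flag in the AE listings and drop out of the separate listing of non-treatment-emergent AEs.

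The SAP handles comparable data differently elsewhere. SAP 4.2.5 classes a therapy as pre-treatment when its stop date precedes first dose, even if its start date is incomplete. SAP 4.2.3 keeps the known parts of incomplete history dates and fills in only the missing day or month. Only the AE rule discards what is known.

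**Working it through.** The plan states no figure on this point, so there is none to reproduce. The check is logical, followed by two simple calculations of scale.

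**1. Rule against definition.** Take an illustrative first dose on 5 April 2022. For each start-date pattern, find the latest onset that the recorded data allow. If it falls before first dose, the definition gives non-TE.

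| Recorded start | Stop date | SAP rule | SAP definition |
|---|---|---|---|
| 28 March 2022 (complete) | any | non-TE | non-TE |
| day unknown, March 2022 | none | TE | non-TE |
| day unknown, April 2022 | 3 April 2022 | TE | non-TE |
| missing | 1 April 2022 | TE | non-TE |
| day unknown, April 2022 | none | TE | undetermined |
| missing | none | TE | undetermined |

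In three of the five incomplete patterns the rule gives the opposite category from the definition. In the other two the timing is unknown and TE is a fair worst case.

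**2. How often the month alone settles it.** Inputs: screening lasts up to 21 days before Visit 1 (Protocol 1.2, Table 1), and first dose comes at the end of the Visit 1 stay, which runs from Day -3 to Day 1. The longest pre-dose window is therefore about 21 + 3 = 24 days. Assume that onset is equally likely on each of the L days before first dose, that the dose day is uniform within the month, and that only the day of onset is missing. An onset k days before dose falls in an earlier month with probability k / 30.4. Averaging over k = 1 to L gives

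share = [(L + 1) / 2] / 30.4

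- L = 7: 4 / 30.4 = 13%
- L = 14: 7.5 / 30.4 = 25%
- L = 21: 11 / 30.4 = 36%
- L = 24: 12.5 / 30.4 = 41%

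A direct count over all first-dose dates from 1 July 2021 to 31 December 2022 agrees: 13.1%, 24.6%, 36.1% and 41.0%. These are shares of pre-dose AEs with a missing day, not of all AEs. Events settled by a stop date come on top.

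**3. Weight of one patient.** Enrolment is 6 to 16 (Protocol 1.1 and 4.1), with 10 as the target in Protocol 9.2. One patient wrongly counted moves an incidence by 100 / n points: 100 / 6 = 16.7, 100 / 10 = 10, 100 / 16 = 6.25. This holds for a preferred-term row only if the patient has no other TEAE with that term.

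**The case against.** The strongest defence is that the sentence is a convention. It follows the definitions, says openly that it is a worst case, is prespecified and programmable, and can err only towards reporting more TEAEs. All of that stands. It does not justify a worst case where the recorded data already settle the question, because there the rule replaces a known answer with the wrong one.

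The second defence is rarity. Onset and resolution dates are required, queries must be resolved (Protocol 8.4.3), data are checked and source-verified (Protocol 10.1.8), and the pre-dose period is short and closely observed, with AE review on each day of the Visit 1 stay. Conditions that predate the trial are not AEs (Protocol 10.3.1). This also stands and is why the point is minor.

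A reader might infer that pre-dose events would inflate the adverse drug reaction and serious AE tables. The documents make that unlikely. The first table needs a judgement of possible or probable relationship, and Protocol 10.3.3 tells the investigator to weigh the timing relative to trial product. SAEs are reported within 24 hours (Protocol 8.4.1), so one with an uncertain onset month would be unusual. A reader might also put a number on the misplaced events. No rate of incomplete dates is given, so any count would be a guess.

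Finally, the fix has a small cost. Protocol 8.4.3 records worsening of an unresolved AE as follow-up to the same event. An AE with a partial but provably pre-dose start date that worsens on drug would therefore leave the TEAE tables. The same AE with a complete pre-dose date is already outside them, so the fix makes the two consistent.

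**Conclusion.** The point holds as a minor one. For AEs whose known month and year, or stop date, show onset before first dose, the SAP 4.4 fallback gives the opposite category from the non-TEAE definition in the same section. It is not a general contradiction in the AE analysis, since where timing is undetermined the rule is appropriate.

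The reach is limited to descriptive safety tables, the TE flags and the non-TEAE listing. The primary and key secondary analyses are untouched, and the direction is always towards over-counting. The actual effect cannot be computed and is probably very small. The 13% to 41% range rests on uniform onset, only the day being missing, and an assumed window of 7 to 24 days; 41% is the top of that range, not a central value. The change is worth making because it is cheap, not because results depend on it.

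**What to change.** Amend SAP 4.4 so that an AE with an incomplete or missing start date is treatment-emergent unless the known parts of the start date, or the stop date, show onset before the day of first dose. Events of undetermined timing keep the worst-case assignment. This extends to AEs the stop-date approach that SAP 4.2.5 already uses for therapies.

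The cost is one sentence and one extra condition in the AE derivation, with no new data. Make the change before database lock and use the same derivation in the interim and final reports. State in the SAP that worsening on drug of an AE with a provably pre-dose start does not make it treatment-emergent, whether its date is partial or complete, so that this consequence is visible.
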